Monitoring or auditing may be performed by means of on-site visits to the MMC clinic or through other communications such as telephone calls or written correspondence. The visits will be scheduled at mutually agreeable times, and the frequency of visits will be at the discretion of CDC. During the visit, any evaluation-related materials may be reviewed and the Investigator along with evaluation staff should be available for discussion of findings. The evaluation may also be subject to inspection by regulatory authorities (national or foreign) as well as the IECs/IRBs to review compliance and regulatory requirements.

Conflicts of Interest

The project investigators and co-investigators report no conflicts of interest.

Reimbursements

Reimbursement for evaluation participation will be offered to compensate clients for the substantial commitment of time and effort required to complete surveys and interviews and to return to the clinic for follow-up visits (Day 7, Day 49, and subsequent follow-up healing visits). It is anticipated that clients will receive transportation and time reimbursement only for their follow-up clinic visits (not for the initial placement visit), transportation and time reimbursement for the qualitative interview, and a HIV prevention kit for participation in the evaluation. Based on an analysis of transportation costs in Shinyanga, and considering the length of times the clients are in the clinic for the VMMC procedure, the value of time and transportation reimbursement is estimated to be between 7-10 USD per visit (16,000-22,000 TZS). If the cost of transportation within Shinyanga, Tanzania increases, the reimbursement may increase to keep pace with the economic environment. However, the reimbursement value will not exceed 12 USD (27,000 TZS) per visit. Reimbursements will be paid to the client upon the conclusion of the visit. For clients under 18, the time and transportation reimbursement will be paid to the client’s guardian accompanying them to the clinic upon the conclusion of the visit.

Some benefits offered for participating in this evaluation (e.g., the provision of condoms and educational materials) may be perceived as additional incentives. During the qualitative interviews conducted with all providers trained to use ShangRing and a random sample of clients, a snack valued at approximately 3 USD (6,500 Tanzanian Shillings) will be offered.

Projected Timeline

The estimated time needed to complete the evaluation, including ethical approvals and report dissemination, is 12 months.

During the preparatory phase, # mid-level providers will participate in a (length in days TBD) training course in good clinical practice. All providers who successfully complete this course will receive formal training on ShangRing device application and removal. The training will be conducted by the trained doctors from countries with previous ShangRing experience (Kenya, Zambia, Uganda).

The detailed timelines for both the preparatory and implementation phases of the evaluation are provided in Tables 2 and 3. Additional details about interactions with clients, including the application and removal of the device and client follow-up, are provided in Table 4.

Dissemination of Findings

Throughout the course of the evaluation pilot key stakeholders in Tanzania will receive a monthly update on the status of the pilot. In Tanzania, key stakeholders include the following: MoHCDGEC, PORALG, RCHMT VMMC TWG, Tanzania PEPFAR TWGs, IntraHealth, and Jhpiego. A monthly update will be provided by IntraHealth. The purpose of these updates is to ensure that all parties that will ultimately assume responsibility for transitioning the pilot to active surveillance under the Ministry are involved. As enrollment approaches completion, discussions will include the transition from evaluation pilot to active surveillance oversight.

Upon completion of primary data analysis and prior to finalizing a final report, findings will be shared with leadership at MOHCDGEC and the national VMMC TWG to ensure the involvement of key stakeholders in the report writing process. Feedback gathered will be used to complete the final evaluation report, which is intended to inform and shape MoHCDGEC policies regarding the use of devices for adult male circumcision in Tanzania. Other means of dissemination will include presentations at international meetings and workshops, and submission of manuscripts to peer reviewed journals. The primary manuscript of the main evaluation results (primary evaluation objectives) will be a project shared by MoHCDGEC, PORALG, CDC, Jhpiego, IHI, and other implementing partners. The final report will be produced in alignment with PEPFAR requirements, and will also be posted in English on a publically accessible website within 90 days of clearance, per PEPFAR regulations. Any presentations/manuscripts on the main evaluation results will assign proper credit and acknowledgment to the contributions of all partners. Presentations/manuscripts on secondary analyses of evaluation data may be undertaken by each partner who has the capability to utilize the data properly and professionally. Requests for data will be made to MoHCDGEC in writing and all collaborating partners will review all presentations or manuscripts for accuracy. No data collected in this evaluation may be published without prior written agreement of relevant staff.

Table 3: ShangRing Implementation Pilot Timeline – Preparatory Phase

Activities	Quarter 4 (July – September 2018)			Quarter 1 (October – December 2018)			Quarter 2 (January – March 2019)		
	July	August	September	October	November	December	January	February	March
Preparatory Phase									
Protocol Development	X								
Human Subjects review and clearance	X	X							
Hire manager and interviewers		X	X						
Interviewer training		X	X						
Data collection: qualitative interviews with clinicians			X	X					
Training of clinicians in Tanzania			X	X					
Data collection: qualitative interviews with clinicians and surveys with ShangRing circumcised males				X	X				
Client follow-up and documentation of outcomes				X	X	X			
Implementation Activities									
									→

[figure not shown]
Table 4: ShangRing Implementation Pilot Evaluation Timeline – Implementation Phase

Activities	Quarter 4 (July – September 2018)			Quarter 1 (October – December 2018)			Quarter 2 (January – March 2019)			Quarter 3 (April – June 2019)		
	July	August	September	October	November	December	January	February	March	April	May	June
Implementation Phase												
Preparatory Activities												
Mid-level provider training in Tanzania			X	X								
Counseling and messaging training					X							
Data collection: qualitative interviews with doctors and mid-level providers						X						
Site Preparation			X	X								
Client follow-up and documentation of outcomes from practice					X	X						
Recruitment of clients for evaluation and device placement					X	X						
Client follow-up and documentation of outcomes				X	X	X						
Data collection: all men at 4 points (immediately after circumcision, at device removal, 49 days post circumcision)				X	X	X	X					
Data collection: 10% of men 28 days after device placement					X	X	X					
Data cleaning and merging						X	X	X				
Write preliminary report								X	X			
Discuss report and findings with key stakeholders									X	X	X	
Present final report to TWG												X

Appendices

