Evaluation Goal:

To evaluate the safety and acceptability of the ShangRing device for nonsurgical circumcision in routine clinical settings, as a part of a comprehensive HIV prevention program for males in VMMC programs.

Evaluation Endpoints:

Primary Endpoint: the proportion of males experiencing mild, moderate and severe adverse events (AEs) associated with ShangRing circumcision procedures, including both intra- and post-operative events, and all device-related malfunctions (e.g., early spontaneous detachment).

Secondary Endpoints:

- Training needed for proficiency using the ShangRing device, including number of procedures to become fully proficient at applying and removing the ShangRing device.
- Client and provider acceptability, client satisfaction, and duration of procedure.
- The percentage of clients clinically healed 49-52 days post-placement of the ShangRing device, and the time at which point all clients are clinically healed.

Evaluation Design

Training Phase: this phase will be used to evaluate the training requirements for implementation by mid-level providers, to preliminarily assess acceptability to providers, and to monitor logistical needs. Each clinician will perform no fewer than 10 ShangRing device placements, and 5 ShangRing removals before start of the next phase (implementation pilot).

Implementation Pilot: following the training period, 575 male clients will be recruited to undergo circumcision with the ShangRing device in the context of routine service delivery.

Data will be collected at up to at least 5 points in time: at enrollment and device placement (day 0), at device removal (day 7), during a follow-up phone call (day 10), in-depth qualitative interviews for 50 purposefully selected clients (day 28), at an in-person follow-up visit to assess wound healing (day 49), and at subsequent weekly visits to assess healing for those not completely healed at day 49.

Upon completion of the implementation pilot, the data will be analyzed and used to assist with policy decisions and recommendations on ShangRing use in adult male circumcision programs.

Section C: Protocol

Introduction

Voluntary Male Medical Circumcision (VMMC), VMMC Devices and ShangRing

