To evaluate the safety and acceptability of the ShangRing for device-based circumcision in routine clinical settings, as a part of a comprehensive HIV prevention program for males aged 13 and older in Tanzania.

Evaluation Objectives

The specific objectives of the proposed implementation pilot is to:

- Describe/assess the safety of the ShangRing device by the occurrence of clinical adverse events (calculated as a rate), when circumcision is performed by trained mid-level providers;
- Ascertain capacity and required clinical capabilities of clinical staff of various cadres to carry out ShangRing procedures;
- Describe/assess male client and provider acceptability of the ShangRing device and process (e.g. need to return to the clinic for device removal, tolerance for leaving device in situ);
- Assess the percentage of clients clinically healed 6 weeks (42 days) following the removal of the device;
- Determine the time at which point all clients are physically healed following the removal of the device.

Primary Endpoint

The primary endpoint related to the goal and objectives of the evaluation is to:

- Measure the incidence of mild, moderate and severe AEs associated with ShangRing procedures including both procedure and post-procedure events, and all device-related malfunctions such as early spontaneous displacement. The primary endpoint will be assessed at device placement, at device removal, 3-days post removal, at the day 49 post-placement healing assessment, and at any unscheduled visit in that time frame. Adverse events will be measured and described in the following ways:
 - Total numbers and types of known AEs occurring among clients, including all severities of AEs (mild, moderate, severe) and serious AEs (see below), including detailed information about all instances of device displacement/detachment/self-removal/malfunction, need for medical attention or intervention, and final outcomes in those experiencing AEs.
 - Total number of clients with known AEs (may be different from above if clients experience multiple AEs), including all severities of AEs and serious AEs.

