 - Total number of clients who fail to return to the circumcision site (or site indicated by service providers) for recommended follow-up (whether removal visit or AE follow-up).
 - Proportion of all men receiving VMMC services at the evaluation sites who choose ShangRing method instead of surgical circumcision.
- Document provider acceptability of ShangRing, to be measured by the following:
 - Provider perceived ease of application, ease of removal, ease of clinical management of adverse events, and preferences in comparison to conventional circumcision methods.
- Document duration of procedures, and problems encountered during procedures and post-procedure care, to be measured by the following:
 - ShangRing application time will be measured, including the overall time the client is on the procedure table, and the time required for discreet application activities: client preparation time (including application of local anesthetic and sizing), marking and device application, and clean-up time.
 - ShangRing removal time will be measured, including the overall time the client is on the procedure table, the time required for discreet removal activities, and time for post removal instructions given to the client.
- The percentage of clients determined by a clinician to be clinically healed 49-52 days post-placement of the ShangRing device (42 days post-removal), and the time at which point all clients are clinically healed.
 - Healing will be documented by evaluation staff, who will take photographs of the client's genital area during the follow-up visits.
 - Healing will meet the definition of clinical healing after VMMC, defined as:
 - "Intact epithelium (unbroken skin) covering the wound as judged by the provider on visual inspection, meaning that none of the following are present: sutures, scabbing, drainage, moisture, gaps between epithelial edges or ulceration."²⁵

Evaluation Design

Overall Design

This implementation pilot is comprised of two phases: a training phase and the main implementation pilot. During the training phase clinicians at the participating sites will be trained in the use of the ShangRing device. Upon completion of the training phase, the main implementation pilot will begin. The implementation pilot is a single arm, open label, prospective cohort evaluation.

Description of Evaluation Populations and Catchment Areas

Shinyanga, Tanzania

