Males who present with exclusion criteria for one of the medical reasons listed above will be referred to the appropriate specialist for management of their conditions. Additionally, any men who have an anatomic contraindication but still want circumcision, can be referred to an urologist for further management. In keeping with standard national practice, clients presenting with specific disease conditions such as STIs or TB may be treated on-site or referred for care elsewhere if appropriate services are not available on site. Furthermore, males who are HIV+ will be assessed to determine if they are on antiretroviral therapy (ART). Those not on ART will be referred for ART.

Client Withdrawal Criteria

A client has the right to withdraw from the evaluation at any time, for any reason, without prejudice to his future medical care by the provider or the health facility (see Appendices V and VI for the client and minor client assent forms). If a client withdraws after consent, but prior to device placement, the client will be replaced until the desired sample size is reached and the data will be excluded from analysis. If a client withdraws after device placement, the client will not be replaced and the existing data will be included in the analysis, but no attempts will be made to collect further data other than that required for clinical documentation of the removal visit. The reason, timing and circumstances of the withdrawal will be documented and analyzed. The client will subsequently not be included among those selected for the day 28 in-person interview, nor will they be asked to return for the day 49 follow-up visit to assess healing. When the client withdraws, they will be informed that they may still return to the clinic for removal of the device as scheduled, and contact the clinic should they have further questions, suffer an AE, or experience other difficulties healing.

A client will be informed in advance that if he wishes to withdraw from the evaluation after ShangRing placement but before scheduled removal, he must still return to the provider for device removal on day 7 for his own health. The client will also be advised that once applied, it is not safe to remove the device before day 5. If the client requests removal on day 5 or 6, it will be removed as requested. The number and reasons for client withdrawals will be recorded and included in the final evaluation report (See Appendix XXII).

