The primary focus of the healing component is to determine the percentage of men that are clinically healed by day 49-52 following the placement of the ShangRing device (42-45 days post-removal), and to determine the time point post-placement at which all clients are clinically healed. All clients will be asked to return for a day-49 healing assessment, where a provider will review the clients wound to determine healing. As noted above, the wound will be considered healed if it meets the clinical definition of healing after VMMC, and will be indicated as such on the CRF. All clients will also have a photograph of their genital area taken at this visit to document healing. If the client is not clinically healed at the day-49 healing assessment, the client will be asked to return for another assessment in one week's time. Weekly healing assessments will continue until all clients are clinically healed.

Table 2: Implementation Pilot: Training and Implementation Phases

Evaluation Component	Sample Size	Endpoints	Methods and Data Collection
Phase 1: Training	Approximately 80-120, depending upon # of providers trained (at least 10 clients per provider)	
Primary endpoints:
 
 - Provider training needs - Provider acceptability 
Secondary endpoints:
 
 - Procedure and removal times 
Training Needs Component
 
Primary endpoints:
 
 - Provider proficiency with applying and removing the device 
Secondary endpoints:
 
 - Adverse events and device-related incidents - Procedure and removal times - Training satisfaction and needs of providers 	
Administered knowledge and theory based tests
 
Supervisor/doctor observation
 
Standardized forms to collect data on adverse events and device-related adverse events
 
Client records
 
Qualitative interview with providers
 
Photographs of the client's genital area, to be taken post-device removal (day 7), and at the day 49 healing assessment visit and at subsequent weekly healing visits

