Follow-Up Visits

Active follow-up will be initiated for clients who fail to return on day 7 post-placement to have the device removed, or for other visits (e.g. AE follow-up) recommended by the ShangRing clinician. Each implementing site will assign staff to conduct follow-up telephone calls and home visits as needed. All active follow-up efforts will be documented on the appropriate forms designed for this purpose (Appendix XI). For clients who fail to return for device removal on day 7, active follow-up will start on day 8. Active follow-up will start with telephone calls to the contact number(s) provided by client and recorded on the locator information sheet at enrolment. An

introductory script for contacting clients by phone is attached as Appendix X. If a client is not reachable through direct voice calls, short text message reminders will be sent to his contact phone number. The reminder text message will include client name and specify the name and phone number of the clinic reaching out to him. The text message will not include the purpose of appointment visit for which the reminder is sent. Up to five calls will be made to reach the client; one per day starting on day 8, and continuing over the next 4 days through Day 12 (5 days post-procedure).

Once contact is made, the staff member will reinforce the importance of device removal and encourage the client to return to the circumcision site. If the client states that he is not able to return by day 9 post-placement, or the schedule day, or does not in fact return by day 9 or the schedule day, the staff member will attempt to verify the addresses provided to schedule an appointment at one of the address locations provided for device removal on day 9, or as soon as possible. If the client has not been successfully contacted by day 9 or the scheduled day, home tracing visits to the address he provided will begin. These will total up to 4 visit attempts on different days if necessary to reach the client.

For clients not under follow-up for AEs who miss scheduled visits other than the day 7 visit, follow-up will be done through phone by text messages or voice calls only, except in exceptional circumstances where a clinician deems physical follow-up necessary.

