Upon conclusion, thank the client for their time and remind them of their visit for the healing assessment in 39 days' time. If the client is one of those selected to participate in the qualitative interview, remind them of the date of the interview.

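### The healing measures run from device removal in the objectives but from placement in the endpoints, and the protocol never reconciles the two for late removals or for the time to complete healing

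*Protocol*

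**What the plan says.** The Evaluation Objectives contain two healing items, both counted from removal: "Assess the percentage of clients clinically healed 6 weeks (42 days) following the removal of the device" and "Determine the time at which point all clients are physically healed following the removal of the device".

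The endpoint in the Executive Summary counts from placement and does not mention removal: "The percentage of clients clinically healed 49-52 days post-placement of the ShangRing device, and the time at which point all clients are clinically healed". The fuller Secondary Endpoints section gives both clocks at once: "clinically healed 49-52 days post-placement of the ShangRing device (42 days post-removal". The Healing Component repeats the day 49 to 52 window but brackets it as 42 to 45 days after removal. It then sets out "to determine the time point post-placement at which all clients are clinically healed". The Analysis Overview refers only to healing by day 49, without a window.

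Removal is scheduled for day 7, but Follow-Up Visits plans for clients who do not return then. Calls run from day 8 to day 12 and home tracing begins on day 9: "These will total up to 4 visit attempts on different days if necessary to reach the client". The same section ties the reminders and the healing visit to placement. A client who does not come on day 49, and has not said he wishes to withdraw, is classed as lost to follow-up.

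Two forms add further versions. In Appendix XIV, the call made three days after removal ends by telling staff to "remind them of their visit for the healing assessment in 39" days. Appendix XII, the follow-up form, labels the healing visit as day 42 after placement.

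**The concern.** An endpoint needs one time origin. Here the objectives use one and the endpoints another, and the link between them is a bracket that silently assumes removal on day 7.

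Three things are at stake. The time at which all clients are healed has no bracket or window linking its two versions, so the reported figure depends on which section the analyst follows. For late removals, the percentage healed would be judged with less healing time after removal than the objective states. And the call script can send a late-removed client to a date on which the follow-up rule has already declared him lost.

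The Photography section says the analysis of healing times will inform pre-procedure counseling on healing and on resuming sexual activity, so a figure with an unclear origin would be passed on to clients.

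**Working it through.** **Inputs.** Scheduled removal: day 7 (Male Circumcision Using ShangRing Device). Objective: 42 days after removal (Evaluation Objectives). Window: days 49 to 52 after placement, bracketed as 42 to 45 after removal (Healing Component). Call: three days after removal, visit in 39 days (Appendix XIV). Visit and loss rule: day 49 (Follow-Up Visits). Form label: day 42 after placement (Appendix XII).

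**The plan's own figure.** Days after removal = days after placement − removal day. For removal on day 7: 49 − 7 = 42 and 52 − 7 = 45. This reproduces the Healing Component's bracket. The single value of 42 in Secondary Endpoints matches only the first day of its window.

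**Late removals.** Let *r* be the day of removal. A day-49 visit is 49 − *r* days after removal. The call script points to day *r* + 3 + 39 = *r* + 42. A visit day *d* meets both windows if 49 ≤ *d* ≤ 52 and 42 ≤ *d* − *r* ≤ 45.

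| Removal day | Days after removal at day 49 | Visit day implied by call script | Days meeting both windows |
|---|---|---|---|
| 7 | 42 | 49 | 49–52 |
| 8 | 41 | 50 | 50–52 |
| 9 | 40 | 51 | 51–52 |
| 10 | 39 | 52 | 52 |
| 11 | 38 | 53 | none |
| 12 | 37 | 54 | none |

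For removal on days 8 to 10 both windows can be met, but only on a day after day 49. Read literally, the follow-up rule has by then classed the client as lost. From removal on day 11, the latest day in the window gives 52 − 11 = 41 days, so 42 is never reached inside it.

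**Time to all healed.** If a client is found healed on day *h* after placement, the two clocks give *h* and *h* − *r*. For removal on day 7 the difference is 7 days: a client healed at the day-49 visit counts as 49 in the Healing Component and 42 under the objective.

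**Form label.** Day 42 after placement is 42 − 7 = 35 days after an on-schedule removal. It is neither 49 days after placement nor 42 days after removal.

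**The case against.** The strongest defence is that the visit schedule itself is consistent. The body of the protocol puts the visit at day 49 after placement for everyone, never books it from the actual removal date, and gives 42 days after removal as the nominal equivalent of day-7 removal. The check-in call is also described as day 10, and 10 + 39 = 49. Clients receive a text on day 42, a second on day 45 if they have not confirmed, and calls on days 47 to 49 if still unconfirmed, so a wrong date from the call may be corrected. Healing is a descriptive secondary endpoint, assessed at day 49 and then weekly, so shifts of 1 to 5 days are smaller than the assessment interval. Follow-Up Visits aims for home removal on day 9 or as soon as possible, so day 12 is an extreme case.

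Most of this stands and limits the point. It does not remove the differing origin in the objectives, the 7-day ambiguity in the time to complete healing, or the day-49 loss rule.

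Three stronger readings are tempting, and the documents do not support them.

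- A reader might infer that early removals are also misjudged, from "If the client requests removal on day 5 or 6, it will be removed as requested". That sentence belongs to Client Withdrawal Criteria, and withdrawn clients are not asked back on day 49. If such a client did attend on day 49, he would be 49 − 5 = 44 or 49 − 6 = 43 days after removal, inside 42 to 45.
- A reader might infer that the clocks agree only for day-7 removal. That is true of single days. As windows, both can be met for any removal day from 4 to 10.
- A reader might infer that the clients affected differ systematically from the rest. The protocol gives no information on this.

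**Conclusion.** The point holds as two unreconciled time origins, not as a visit schedule on the wrong clock. The time at which all clients are healed differs by 7 days for on-schedule clients, and otherwise by the removal day. For removal on days 8 to 12, a day-49 visit falls 1 to 5 days short of the objective's 42. From day 11 the day 49 to 52 window cannot supply 42 days at all. The call script and the loss rule conflict for every removal after day 7 if both are followed literally and the call is made three days after actual removal.

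The protocol gives no number of late removals, so the effect on the percentage healed cannot be computed and may be small. The correction should still be made, because it settles what a stated endpoint means and how attendance is classified.

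**What to change.** Use placement as the origin for both healing measures, as the Executive Summary, the Healing Component and Table 2 largely do already, and reword the two items in Evaluation Objectives to match. State the day 49 to 52 window once and refer to it elsewhere, including in the Analysis Overview. Present the days-after-removal figure as nominal for day-7 removal.

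In Follow-Up Visits, count attendance on any day of the window as assessed rather than lost to follow-up. In Appendix XII, correct the day-42 labels to the chosen schedule. In Appendix XIV, replace the 39-day interval with the calendar date of the booked visit.

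Derive healing status and timing from the recorded placement, removal and visit dates, and report days since removal alongside. This names the analysis origin only and leaves clinical management untouched.

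The cost is wording in the objectives, the follow-up rule and two forms. No new data are needed: Appendix XII already records the visit date, the placement date and the days from placement to removal.
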